## **1. Background and Significance**

Non-pharmacological early-intervention strategies to slow the growing epidemic of age-related cognitive decline and dementia, and their well-established impact on functional outcomes, must include the targeting of executive function (EF). EF encompasses several essential higher cognitive skills, including attentional control, planning, response inhibition and working memory. In addition to portending Alzheimer's disease, executive dysfunction in older adults is associated with impaired gait and balance and higher fall risk, which significantly decrease functional independence and overall quality of life (QOL).

Exercise is considered a promising intervention for preservation and restoration of cognitive function in older adults, including EF, with literature reviews suggesting that multimodal training that integrates physical and cognitive training may have advantages over unimodal interventions. Tai Chi (TC) is an increasingly popular multimodal mind-body exercise that incorporates physical, cognitive, social, and meditative components within the same activity. Recent meta-analyses show that TC is a promising intervention for EF and global cognitive function in older adults. In several studies, TC was found to be superior to conventional exercise.

The CDC and many other agencies endorse TC. Yet surprisingly, a comprehensive 2014 national survey found that only 1.2% of the entire adult population reported using TC for health, suggesting potential limitations in access to training programs. Limited access to community training programs is also indicated by the fact that a significant percentage of survey respondents reported learning TC from online or video courses.

During phase I of the SBIR NIH grant, we developed algorithms based on information gathered from wearable sensors to estimate adherence, proficiency, and safety metrics. During the non-clinical stages of phase II, we developed a complete beta-version of the Tele-TC platform. The Tele-TC system consists of a set of 5 wearable sensors and an app installed on a commercially available tablet.

As a preliminary step toward designing a future study to assess the clinical benefits of the Tele-TC platform as a training system for elderly with mild cognitive impairments, we herein propose to assess:

- If the system enables monitoring longitudinally of adherence, proficiency, and safety.
- If the system is acceptable and user-friendly for its intended use in the home setting.
- As an exploratory aim: if a 12-week training program using the Tele-TC platform leads to improvements in cognitive function, balance, physical activity, self-efficacy, health-related quality of life, and gait.

If this preliminary study leads to positive results, we will embark on a follow-up study to assess the potential clinical benefits of using the technology as part of a clinical intervention on cognition, balance, physical activity, gait, self-efficacy, and health-related quality of life.

## 2. Specific Aims and Objectives

The overall goal of the study is to test the delivery of a novel Tele-Tai Chi (TC) intervention in a single-arm feasibility study for community-dwelling TC-naïve older adults with mild cognitive impairment (N=20 total). We will assess feasibility and acceptability measures of the Tele-TC intervention and its specific components through both qualitative and quantitative feedback, as well as the systematic tracking of adherence data to inform future trials and potential clinical use of the Tele-TC system. We will also explore changes in clinically relevant outcome measures including cognitive function, physical activity, self-efficacy, quality of life, balance, gait, and evaluate changes in TC proficiency.

### Primary aims

- Aim 1: *To evaluate the feasibility, acceptability, and safety of a novel home-based Tele-TC intervention by tracking recruitment, retention, adherence, and adverse events.*
  - Hypothesis 1: We will be able to recruit 20 older adults with mild cognitive impairment and limit withdrawals to 20% or less.
  - Hypothesis 2: Participants will complete >60% of recommended Tele-TC sessions.
  - Hypothesis 3: Protocols for assessing safety can be developed and reliably administered, and preliminary evidence will support Tele-TC can be delivered safely.

**Figure 1: Study system.**

### **Exploratory aims**

- Aim 2: *To evaluate changes in the level of proficiency of TC during a 12-week simplified TC program using the Tele-TC platform at home.*
  - Hypothesis 1: We will be able to collect reliable data on TC proficiency during Tele-TC use by study participants.
  - Hypothesis 2: Proficiency scores will improve over 12 weeks of training using the Tele-TC program supporting protocol learnability.
- Aim 3: *To gather feedback from end-users on ease of use of the Tele-TC platform.* We plan to collect feedback from elderly subjects to assess if the system is user-friendly enough to envision its use in a clinical setting.
  - Hypothesis 1: We will be able to collect reliable data on ease of use of the platform using qualitative and quantitative measures.
- Aim 4: *To explore changes in clinically relevant outcome measures including cognitive function, physical activity, self-efficacy, quality of life, balance, and gait.*
  - Hypothesis 1: We will be able to collect reliable outcomes data at each testing visit.
  - Hypothesis 2: We will see clinically relevant changes in outcomes measures at 12 weeks.

### **3. General Description of Study Design**

As a preliminary test of our platform's suitability as a home-based TC program for people with mild cognitive impairments, we will recruit a convenience sample of 20 community-dwelling TC-naïve older adults with mild cognitive impairments into a single-arm longitudinal study of home-based TC learning, combined with remote and in-person data collections. In-person data collection will take place at the Spaulding Rehabilitation Hospital Motion Analysis Laboratory.

### **4. Subject Selection**

#### **Inclusion criteria:**

Eligibility criteria are purposefully broad to maximize generalizability of the study results. To be eligible to participate in the study, individuals will have to meet the following criteria:

- Men and women between 60 and 85 years old
- TC naïve (never practiced TC)
- With mild cognitive impairments (Montreal Cognitive Assessment (MoCA)-Blind score between 17 and 13).
- Self-reported ability to walk continuously for 15 minutes without an assistive device
- Working email address
- Prior experience with and current access to a computer, smart phone or tablet device

#### **Exclusion criteria:**

Individuals will not be eligible to participate in the study if they exhibit any of the following:

- Chronic neuromuscular conditions (e.g. Parkinson's disease, multiple sclerosis, stroke)
- Acute medical conditions requiring hospitalization within the past 6 months or that could interfere with safely participating in the study
- Active cancer
- Significant musculoskeletal conditions requiring chronic use of pain medication
- Significant cognitive impairment (Diagnosed with dementia (self-reported), or Montreal Cognitive Assessment (MoCA)-Blind score < 13)

All subjects will be recruited by IRB approved study staff for this protocol. Recruitment strategies will include the use of the following sources:

- Physicians and therapists may refer interested patients to the study (we will provide physicians and therapists with study flyers and brochures to inform clinicians of the study details).
- Flyers posted in outpatient clinics, therapy gyms, and public spaces both inside and outside the hospital campus.
- PowerPoint presentation to inform clinicians and prospective participants about the study.
- Contacts at local senior and community centers.
- Recruitment letters sent to patients within the Partners network who have previously expressed interest for participating in research studies.
- Via contacts with patients who have consented to be directly contacted in the Partners Research Patient Data Registry (RPDR) or RSVP for Health.
- Via contact to the patients listed for direct contact in the Partners Research Patient Data Registry (RPDR) and Patient Gateway (via research invitation letters), as appropriate. A manual medical record review will be performed on all potential participants identified in this manner to ensure they are appropriate candidates for participation.
- Via targeted medical records review (i.e. current inpatients/outpatients within relevant departments at MGB institutions) using EPIC. Potential participants identified in this manner will be contacted through Patient Gateway (via research invitation letters) or mailed letters as appropriate.
- Via the Partners Clinical Trials (Rally) website.
- Via newsletters or community boards such as the Osher Center for Integrative Medicine newsletter.

Recruitment will also occur through the Spaulding Research Registry, which is a database of persons who have had a stroke, traumatic brain injury, or spinal cord injury and wish to be considered for participation in research studies at Spaulding Rehabilitation Hospital - Boston and other affiliated Harvard institutions. Patient information kept in the registry includes name, contact information, diagnosis with date of onset, laterality and language involvement for stroke, level of injury for SCI, severity for TBI, date of birth and gender. In addition, a record of referrals to specific studies, with dates and enrollment status, will be maintained for each registry member. The information is patient reported and is maintained in an encrypted, Mass General Brigham approved database. When investigators with IRB approved protocols request assistance

in identifying potential subjects, the Registry will create a list of those in the database with the desired characteristics. The Investigator will provide a letter describing the study which the Registry will send to those on the list. Patients receiving these letters contact the Investigator directly to pursue potential participation in the study.

Subjects who are interested and willing to participate in the study will undergo an initial screening over the phone or in-person to determine their eligibility. Subjects who underwent the phone screening and qualify will be sent study information and will be scheduled to visit the lab where they will undergo a final screening in-person to assess whether they meet all the inclusion and exclusion criteria. Testing will only be performed after obtaining signed consent from the subject.

The study entails no cost to the subject. We will cover parking costs for all participants who park at the SRH garage while taking part in the study. Participants will be compensated for their time at study completion.

## **5. Subject Enrollment**

The study procedures will be carried out remotely using a Zoom Enterprise Partners account or in person. Prior to the first visit, we will perform a phone screening to determine eligibility of prospective study volunteers. Individuals will be informed that identifiable information may be recorded during the phone screening. If a subject is deemed eligible, identifiable information (e.g. name, contact info) will be collected, and an informed consent form will be emailed to subjects for review. Baseline testing at a future date will be scheduled.

Eligible subjects will undergo the informed consent process in person, by phone or on Zoom Enterprise with a trained research assistant at the beginning of the baseline testing visit. Once consented, subjects will undergo baseline assessments (visit #1) in person using REDcap Survey. After baseline testing, subjects will participate in the Tele-TC intervention, with recommended training sessions at least three times a week, along with two or more supplementary one-on-one live sessions (lasting upwards to 45 minutes) with TC instructors. TC proficiency using wearable sensors will be assessed at visit #1 baseline, at two follow-up assessments (visit #2 and visit #3) at approximately 4 and 8 weeks, and at a final assessment (visit #4) at 12 weeks. A semi-structured qualitative interview will also be performed at visit #1 and #4.

[figure not shown]
## **6. STUDY PROCEDURES**

Below, we provide a detailed description of the study procedures.

### **1. Screening and Informed Consent (Visit #1A)**

Prior to beginning the consent process, study staff will ensure subjects' eligibility using a brief questionnaire. This, in addition to the phone screening done as part of the recruitment process prior to the first visit, will ensure the eligibility of prospective study volunteers. The phone

screening is not only undertaken to allow researchers to confirm the subjects' eligibility, but it is also an opportunity for the volunteer to ask any additional questions they might have regarding the study. The phone screen includes administration of the Montreal Cognitive Assessment (MoCA)-Blind, an adapted version of the original MoCA, a validated, rapid screening instrument for mild cognitive impairment. Informed consent will be obtained by trained study staff in

**Figure 2: Flow Chart of the study.**

person. Study staff will explain all the study procedures, equipment, and the risks associated with them as outlined in the informed consent form (ICF). The devices will be provided to the subjects after consent.

Subjects will be provided among others with two mobile devices and requisite chargers, a tablet travel stand, tripod, two GeneActiv watches, 5 wearable sensors, each of them with elastic bands and with chargers and wires. Of the two mobile devices, one will be used to interact with the developed TC app and the other will be used an extra mobile device and stand for virtual visits and video recording.

## 2. Assessments (Visits #1B, #2, #3 and #4)

At *Visit #1B*, subjects will be instructed in how to use the tablet-based Tele-TC program. The mobile devices and the sensors will be provided to each participant and will be preprogrammed with all required software. It is worth emphasizing that, as part of the consent process, all subjects will be asked permission to be videorecorded during the assessments via Zoom Enterprise.

Visits will be divided into two components: 1) clinical assessments and 2) instrumented monitoring of TC performance.

The following clinical assessments will be performed during *Visits #1B and #4*.

The following questionnaires will be provided to the subjects through REDcap Survey with an email link. It will take around 45 minutes to complete all of the questionnaires.

- *Activities Specific Balance Confidence (ABC)*: 16-item self-report measure in which patients rate their balance confidence for performing activities.
- *PROMIS® (Patient-Reported Outcomes Measurement Information System) 29 (PROMIS-29)* instrument: 29-item questionnaire assessing each of the following domains: anxiety, depression, fatigue, physical function, pain interference, pain intensity, sleep disturbance, and ability to participate in social roles and activities. The instrument contains four items from each primary domain plus a single pain intensity rating.
- *Physical Activity Scale for the Elderly (PASE)*: self-reported level of physical activity in individuals aged 65 years or older during the previous 7 days.
- *Exercise Self-efficacy Questionnaire (SEE)*: A 9-item questionnaire that focuses on the self-efficacy expectations for exercise for older adults; specifically, the ability to continue to exercise despite barriers.

*Clinical assessments which take around 15 minutes will include tests such as:*

- *Trail Making Test A/B*: Executive function will be assessed using the Trail Making Test. Participants will be timed while sequentially connecting a series of numbered circles (part A), as well as connecting an alternating series of numbers and letters (part B). The adjusted trail making score (i.e., part B minus A, sec) is sensitive to changes in executive function and frontal lobe pathology in older adults. The trail making Test will be camera-recorded.
- *Controlled Oral Word Association Test (COWAT)*: examines working memory span. COWAT requires the participant to produce as many words as possible that begin with a given letter of the alphabet (F,A,S). There is 1 minute allowed for each of the three letters. The score is the sum of all acceptable words produced in the three trials. COWAT has good reliability and validity. The test will be audio-recorded and transcribed to ensure accurate collection of subjects' verbal responses.
- *Digit Span Test*: widely used measure of short-term memory, i.e. the number of digits a person can absorb and recall in correct serial order. Two trials of eight number sequences

are read aloud. The number sequences start out easy, with just two numbers, and get progressively more difficult, the last being nine digits. Scores are based on the number of sequences correctly recalled (i.e., until the participant consecutively fails two trials of the same digit span length). BDS has good reliability and validity.

- *Grip Strength:* we will measure the grip strength of both upper limbs using a hand grip dynamometer. We will repeat the measure three times.
- *Instrumented and camera-recorded monitoring of balance in each leg separately:* Subjects will be asked to stand on one leg for 30 seconds.
- *Instrumented and camera-recorded Timed-Up-and-Go:* Subjects will be asked to stand up from a chair, walk at their normal speed around a cone, turn around, and come back to sit in the chair.
- *Instrumented and camera-recorded Timed-Up-and-Go dual task:* Subjects will be asked to complete the previous task while counting backwards by three.
- *Instrumented and camera-recorded Sit-to-Stand:* Subjects will be asked to stand up from a chair while keeping their arms crossed across their chest during 30 seconds.
- *Instrumented and camera-recorded monitoring of balance in both legs* with feet shoulder-width apart and as close as possible without touching.
- *Instrumented and camera-recorded monitoring of gait:* Subjects will be asked to walk back and forth for 2 minutes.
- *Instrumented and camera-recorded monitoring the miniBEST:* It is a shortened version of the Balance Evaluation System Test (BESTTest). It is a 14-item test scored on a 3-level ordinal scale. It aims to target and identify different balance control systems.

Instrumented and camera-recorded monitoring of TC performance will be performed during Visits #1B, #2, #3 and #4:

- Participants will be instrumented with 5 sensors (one on each limb and one on the trunk) and they will be following the instructions from the Tele-TC platform.

Study staff will use Zoom to communicate with subjects during the visits done remotely. The performance of TC exercises will also be videorecorded and scored using the proficiency metric described in our preliminary studies section to provide a gold standard. We will try to use the sensors during the remote visits, but if it is not possible, we will document the reasons and continue the TC exercises only with video.

Subjects will be asked to don one Smart GeneActiv watch by ActivInsights\* on their wrist to monitor activity during approximately a week after visits #1B and a week before visit #4.

We will ask the participants to send the GeneActiv back to the lab after wearing it. We will be sending another GeneActiv about two weeks before visit #4.

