***3. TC Training Sessions the Tele-TC Platform (12 weeks)***

Study volunteers will participate in a 12-week simplified TC program that we have used in multiple prior clinical studies. In this pilot study, the intervention will be delivered via our platform-based application. All participants will be provided with a tablet with the Tele-TC software installed. The structured intervention, designed for older adults, emphasizes essential TC movements that are easily comprehensible and can be performed repetitively in a flowing manner. The protocol includes up to six core TC movements based on the traditional Cheng Man-Ch'ing's Yang-style short form. Additionally, a complementary set of traditional TC warm-up exercises that focus on loosening the physical body, incorporating mindfulness and imagery into movement, promoting overall relaxation, and coordinating breathing awareness are included. Chairs are used in the protocol for a subset of seated warm-up exercises, as well as for stability and rest as needed. Participants will be asked to practice the protocol (45-60 min) at home for at least 3 days a week for 12 weeks. In addition to data on practice frequency, duration, protocol adherence and training proficiency being automatically collected through our platform, a weekly REDcap survey will be used to monitor adverse events. The TC program will also include 2 or more live instructional sessions via Zoom with a TC instructor.

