## **9. Statistical Analysis**

Descriptive statistics will be derived for all the above-described clinical assessment outcomes and correlations will be sought with the sensor-based estimates of the metrics of adherence, proficiency and safety derived using the previously developed algorithms. Exploratory statistical analyses will be performed to power future clinical studies aimed to test the relationship between the proposed metrics of adherence and proficiency and the clinical outcomes of the intervention. Whereas conclusive statistical analyses to explore such correlations are beyond the scope of the proposed project, the data collected in this pilot study are expected to provide justification for a future trial aimed to assess the efficacy of the Tele-TC Platform as a training system for older adults with mild cognitive impairments.

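### The PASE change counts the prescribed Tai Chi, so it measures total activity and its planned correlation with adherence is partly built in

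*Combined protocol and SAP*

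**What the plan says.** Section 6, item 2 (Assessments) opens its list with "The following clinical assessments will be performed during" Visits #1B and #4. PASE is in that list, as the "self-reported level of physical activity in individuals aged 65 years or older during the previous 7 days".

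Section 5 (Subject Enrollment) fixes the order of events: "After baseline testing, subjects will participate in the Tele-TC intervention", with Visit #4 placed "at a final assessment (visit #4) at 12 weeks". Section 4 admits only people with no Tai Chi experience. Section 6, item 3 sets the programme: "Participants will be asked to practice the protocol (45-60 min) at home for at least 3 days a week for 12 weeks". The same item says the platform records practice frequency and duration automatically.

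Section 6, item 7 lists the baseline to post-intervention change in PASE, and the activity level, among the exploratory outcomes. The primary outcomes there are retention, adherence and the System Usability Scale. Section 9 derives descriptive statistics for the clinical assessment outcomes and adds that "correlations will be sought with the sensor-based estimates of the metrics of adherence, proficiency and safety". It intends these exploratory analyses to help power later studies of how adherence and proficiency relate to clinical outcomes.

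The protocol does not tell participants whether to count Tai Chi in PASE, does not separate programme from other activity, and states no gap between the last practice week and Visit #4.

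**The concern.** The two recall weeks differ by design. The first contains no prescribed sessions and the second contains a full week of them. Aim 4 treats physical activity as a clinically relevant outcome, but a change score built this way mixes two things: the sessions themselves, which adherence already reports, and any change in what participants do outside the sessions. The plan reports only the sum, and with one arm there is no control group to show what other activity would have done.

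The correlation is the more serious part. Adherence measures the sessions done, and those sessions are also a component of the activity score. Some positive correlation is expected even if adherence has no relation to the rest of a participant's activity. Section 9 wants this kind of relationship as an input to the next trial. A part-whole overlap is a bias, so a larger sample would not remove it.

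**Working it through.** The plan gives no SD, correlation or power figure for PASE, so there is nothing of its own to reproduce.

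**1. Timing.** The baseline week contains about 0 minutes of Tai Chi (no prior practice; training follows baseline testing). The Visit #4 week is about week 12 of 12.

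**2. Prescribed minutes in the Visit #4 week** (Section 6, item 3: at least 3 days, 45-60 min).
- Full adherence: 3 × 45 = 135 and 3 × 60 = 180 min/week.
- At 60%, the threshold in Aim 1, Hypothesis 2: 0.6 × 135 = 81 and 0.6 × 180 = 108 min/week.

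**3. What the change can show.** Change in total = Tai Chi minutes + change in other activity. A total change of 0 fits no sessions with other activity unchanged (0 + 0). It equally fits 81 minutes of Tai Chi with 81 minutes of other activity given up (81 − 81). The total cannot tell these apart.

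**4. Built-in correlation.** Let change in other activity have mean 0, SD s, and no relation to adherence. Then

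r = ρ × SD_TC / √(SD_TC² + s²), with SD_TC = prescribed minutes × SD of adherence,

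where ρ links overall adherence to week-12 adherence. Assumptions not in the documents: SD of adherence 0.2 to 0.3, ρ from 0.5 to 1, s from 30 to 480 min/week.

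- Lowest: SD_TC = 135 × 0.2 = 27, ρ = 0.5, s = 480: 0.5 × 27 / √(27² + 480²) = 0.03.
- Highest: SD_TC = 180 × 0.3 = 54, ρ = 1, s = 30: 54 / √(54² + 30²) = 0.87.
- Middle case: SD_TC = 157.5 × 0.25 = 39.4, ρ = 1.

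The last column is the simulated chance of p < 0.05 from the overlap alone in the middle case (mean adherence 0.7, 4,000 simulated trials per cell). It uses n = 20 as planned and n = 16 after 20% withdrawals (20 × 0.8).

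| s (min/week) | r, range | r, middle case | p < 0.05, n = 16 / n = 20 |
|---|---|---|---|
| 30 | 0.33-0.87 | 0.80 | 98% / 99% |
| 60 | 0.21-0.67 | 0.55 | 62% / 73% |
| 120 | 0.11-0.41 | 0.31 | 21% / 26% |
| 240 | 0.06-0.22 | 0.16 | 9% / 11% |
| 480 | 0.03-0.11 | 0.08 | 6% / 7% |

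The two-sided 5% critical r is 0.50 at n = 16 and 0.44 at n = 20.

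**5. With sessions excluded.** The shift in step 2 and, under this model, the built-in r in step 4 both fall to 0.

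**6. The watch.** Section 6, item 2 has it worn for about a week following Visit #1B and again in the week preceding Visit #4. On that schedule both windows fall after training starts. Both can contain sessions, and there is no untrained baseline.

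**The case against.** **Total activity is a legitimate target.** Aim 4 speaks of physical activity, not of activity outside the programme. Whether total activity rises during a home exercise programme is a fair exploratory question, and total PASE addresses it. This stands. The defect is that the plan does not say which quantity it means and treats the total like any other outcome when correlating with adherence.

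**Substitution nets out.** A reader might infer that PASE must improve whenever sessions are done. The documents do not support that: by step 3, full replacement leaves the total flat, and larger displacement makes it fall. A rise does carry some information beyond adherence, namely that the sessions were not fully offset.

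**The size is assumed.** A reader might also infer a large artefact. With an SD of Tai Chi minutes of 60, r would be 0.71, 0.45 or 0.24 at s = 60, 120 or 240. But that SD implies an adherence SD of 60/180 = 0.33 to 60/135 = 0.44, which is close to all-or-none practice, and the table gives lower values in the middle case. If other activity is very variable, the overlap hardly matters. The figures are also in minutes, and the documents give no PASE items or weights.

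**The analysis is exploratory.** Section 9 disclaims conclusive correlation analyses and does not single out PASE. This limits the consequence. It does not remove the bias from an estimate meant to inform future powering.

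**Telling participants to leave Tai Chi out at Visit #4 would harm the comparison.** It would change the instructions between the two visits being compared and add a recall burden for people with MoCA-Blind scores of 13 to 17. This objection stands, so the fix below does not do it.

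**Conclusion.** The point holds as one of labelling and interpretation, and of one correlation. The PASE change is a change in total activity that includes at least 135-180 min/week of prescribed Tai Chi (81-108 at 60% adherence) at one visit and none at the other. It cannot separate added from replaced activity. Its correlation with adherence is partly built in, by an unknown amount: about 0.03 to 0.87 across the assumed SDs, in minutes.

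This rests on three readings. First, Tai Chi counts as activity in PASE, which follows from the protocol's description of the scale. Second, Visit #4 falls within about a week of the last practice; item 7's term post-intervention could suggest a gap, but Section 5 says 12 weeks and none is stated. If Visit #4 came more than 7 days after practice stopped, the overlap would vanish. Third, the correlation uses either the change or the Visit #4 level; Section 9 does not say which, and the overlap affects both.

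The documents do not support the stronger conclusions that the PASE change is invalid or that the correlation is mainly artefact. Retention, adherence and usability, the primary outcomes, are not affected.

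**What to change.** 1. Keep the PASE instructions identical at both visits, and label the change as total activity including programme sessions.
2. Report platform-logged Tai Chi minutes for the Visit #4 recall week beside it.
3. For the GeneActiv outcome, present activity with and without the platform-logged session times, handled the same way in both windows. State that both windows fall after training starts, so this is not a change from an untrained baseline.
4. In Section 9, state that the correlation of adherence with any activity measure containing the sessions will not be used as evidence or as a planning input. Use session-excluded watch activity for that purpose.

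This uses only data already collected and changes no visit, questionnaire, training schedule or sample size. The costs are slightly more analysis, reliance on accurate session time stamps, and an activity result that may look less favourable. Someone who swapped walking for Tai Chi would show a fall in session-excluded activity with the total unchanged, which is why both figures should be shown.
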